6.3. Lifestyle Restrictions

Participants will be instructed to abstain from sexual activity from the Baseline Visit through the TOC Visit to prevent possible re-infection with NG. If a participant refuses to abstain and is sexually active, male participants as well as male partners of female participants, of both childbearing and nonchildbearing potential, must use a male condom during intercourse from the Baseline Visit through completion of the TOC Visit. Details for contraception requirements are included in Appendix 6.

6.3.1. Meals and Dietary Restrictions

Gepotidacin and azithromycin should be taken with food (a meal or snack) (see Section 7.1).

6.4. Screen Failures

Screen failures are defined as participants who consent to participate in the clinical study but are not subsequently randomized. Participants who are screen failures are not allowed to be rescreened for the same infection episode; however, participants who were screen failures for an earlier infection episode may be newly screened for a second infection episode ≥ 4 weeks later and participate in the study if they meet all of the inclusion and exclusion criteria. A minimal set of screen failure information is required to ensure transparent reporting of screen failure participants to meet the Consolidated Standards of Reporting Trials (CONSORT) publishing requirements and to respond to queries from regulatory authorities. Minimal information includes demography, screen failure details, eligibility criteria, and any SAEs.

7. TREATMENTS

All doses of oral study treatment should always be taken after food consumption and with water. Study treatment is defined as any investigational treatments or marketed products intended to be administered to a study participant according to the study protocol.

7.1. Treatments Administered

Study Treatment Name:	Gepotidacin	Ceftriaxone	Azithromycin ^a
Dosage Formulation:	Tablets containing gepotidacin and inactive formulation excipients	Sterile powder for reconstitution with appropriate diluent	Tablets ^a
Unit Dose Strengths/ Dosage Levels:	4 × 750-mg tablets	500-mg equivalent	2 × 500-mg tablets ^a
Route of Administration:	Oral	IM	Oral
Dosing Instructions:	
Administer first oral dose at the study site. Participant self-administers the second dose as an outpatient 10 to 12 hours after the first dose; however, for participants who weigh <50 kg or have moderate renal impairment, the second dose should be taken approximately 12 hours after the first dose
 
Dose 1: 3000 mg – 4 tablets
 
Dose 2: 3000 mg – 4 tablets
 
Each dose should be taken after food consumption and with water.
	
Administer one 500-mg IM dose at the study site (volume administered will be dependent on the amount of diluent^b added and resulting concentration; see Study Reference Manual).
	
Administer one 1-gm oral dose at the study site.
 
Dose should be taken after food consumption and with water.

Study Treatment Name:	Gepotidacin	Ceftriaxone	Azithromycin ^a
Packaging and Labeling:	Gepotidacin tablets will be provided in bottles. Each bottle will be labeled as required per country requirement.	Ceftriaxone will be provided by PPD and labeled as required per country requirement.	Azithromycin tablets ^a will be provided by PPD and labeled as required per country requirement.
Manufacturer:	CCI	May be sourced locally or centrally within individual countries but will be supplied by PPD and labeled as per the regulatory requirements in all participating countries.	May be sourced locally or centrally within individual countries but will be supplied by PPD and labeled as per the regulatory requirements in all participating countries.

IM=intramuscular.

- a. The total oral dose of azithromycin must be 1 gm. Based on locally or centrally sourced available supplies and tablet/capsule strengths, the number of tablet/capsules may be adjusted to reach the 1-gm dose of azithromycin.
- b. Study sites will be responsible for procurement of diluent and injection supplies.

The labeling, distribution, procurement, and/or drug returns for comparator investigative products were supported by Almac US, Almac UK, PPD Athlone (Germany and Spain), Flinders (Australia), World Courier Mexico, Clinigen (Australia, EMEA, and US), Bionical LTDA (UK), and Oncomedic (Mexico).

7.2. Dose Modification

The study design does not allow for dose modifications.

7.3. Method of Treatment Assignment

Participants will be stratified by sex and sexual orientation combination (MSM, MSW, or females) and age (<18 years, ≥18 to 65 years, or >65 years) to ensure that treatment groups are balanced within each category. The MSM category will include MSM and bisexual males (i.e., male participants who have sex with both males and females). Within each stratum, participants will be centrally randomized in a 1:1 ratio to either gepotidacin or ceftriaxone plus azithromycin using an interactive response technology (IRT) in accordance with the randomization schedule generated by or under the direction of GSK's Clinical Statistics. Before the study is initiated, information and directions for the IRT will be provided to each study site.

Each participant scheduled to receive study treatment will receive a randomization number at the time of randomization. This randomization number will be used to identify the participant and indicate the treatment to be administered to that participant.

For those participants randomly assigned to gepotidacin, the first dose will be administered at the study site during the Baseline Visit and the second dose will be dispensed to participants during this visit for self-administration 10 to 12 hours after the

first dose (see Section 7.1). Participants randomly assigned to ceftriaxone plus azithromycin will be administered a single IM dose of ceftriaxone plus a single oral dose of azithromycin during the Baseline Visit.

Returned gepotidacin should not be re-dispensed to other participants.

7.4. Blinding

This is an open-label (sponsor-blinded) randomized study. The specific treatment to be taken by a participant will be assigned using an IRT using central randomization. The study site will contact the IRT prior to the start of study treatment administration for each participant. The study site will record the treatment assignment on the applicable electronic case report form (eCRF), if required. Potential bias will be reduced by the use of central randomization.

The GSK SRT, which will monitor safety data instream, will remain blinded to participant treatment assignment throughout the study (see Appendix 3). A Microbiology Review Team will monitor blinded pathogen identification and susceptibility data instream as well as the number of participants eligible for the micro-ITT Population. Blinded monitoring of pathogens will be conducted, to determine whether end-of-study targets are likely to be achieved. Provision will be made for a limited degree of unblinding of a minority of participant sample data should this be viewed as appropriate for planning closure of trial enrollment. Procedures will be described in a separate microbiology sample monitoring plan, and no impact on trial integrity is expected.

7.5. Preparation/Handling/Storage/Accountability

No special preparation of gepotidacin or azithromycin is required.

A pharmacist or other qualified professional will prepare the ceftriaxone solution using a fixed volume of an appropriate diluent to reconstitute the ceftriaxone powder. Full details of the methods and materials required for ceftriaxone solution preparation are provided in the SRM.

The following considerations must be made with regard to study treatment preparation, handling, storage, and accountability in this study:

1. The investigator or designee must confirm appropriate temperature conditions have been maintained during transit for all study treatment received and any discrepancies are reported and resolved before use of the study treatment.
2. Only participants enrolled in the study may receive study treatment and only authorized study site staff may supply or administer study treatment. All study treatments must be stored in a secure, environmentally controlled, and monitored (manual or automated) area in accordance with the labeled storage conditions with access limited to the investigator and authorized study site staff.
3. The investigator, institution, or the head of the medical institution (where applicable) is responsible for study treatment accountability, reconciliation, and record maintenance (i.e., receipt, reconciliation, and final disposition records).

4. Further guidance and information for the final disposition of unused study treatment are provided in the SRM.

Under normal conditions of handling and administration, study treatment is not expected to pose significant safety risks to the study site staff. For ceftriaxone solution, take adequate precautions to avoid direct eye or skin contact and the generation of aerosols or mists. In the case of unintentional occupational exposure, notify the monitor, medical monitor, and/or GSK study contact.

A Material Safety Data Sheet or equivalent document describing occupational hazards and recommended handling precautions either will be provided to the investigator, where this is required by local laws, or is available upon request from GSK.

7.6. Treatment Compliance

- When the individual dose for a participant is prepared from a bulk supply, the preparation of the dose will be confirmed by a second member of the study site staff.
- Participants dosed at the study site will receive study treatment (oral dose of gepotidacin or single IM dose of ceftriaxone plus an oral dose of azithromycin) directly from the investigator or designee, under medical supervision. The date and time of each dose administered in the study site will be recorded in the source documents and reported in the eCRF. The dose of study treatment and study participant identification will be confirmed at the time of dosing by a member of the study site staff other than the person administering the study treatment.
- Participants will self-administer the second oral dose of gepotidacin as an outpatient (see Section 7.1). Compliance with gepotidacin will be assessed by contacting the participant via telephone, email, or text message. The participants should confirm that the second dose was taken. Study site staff will also query the participant during the TOC Visit and document whether the second dose was taken. A record of the number of gepotidacin tablets dispensed to each participant must be recorded and reconciled with study treatment and compliance records. The date and time of each dose will also be recorded in the eCRF.

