- c. Participants will be instructed to return to the study site from Day 14 to 21 for a Follow-up Visit. The investigator and/or study site staff should make every effort to ensure the participant returns for this visit. If the participant is unable to return to the study site, the visit assessments may be completed via telephone, with the exception of assessments requiring sample collection for laboratory testing.
- d. Refer to the Study Reference Manual for information to collect for social and sexual history.
- e. See Table 2 for collection of bacteriology samples. Also refer to the laboratory manual.
- f. See Table 2 for collection of NAAT assay samples. Also refer to the laboratory manual.
- g. A complete physical examination will be performed at the Baseline Visit and a gonorrhea-focused examination will be performed at the TOC Visit (see Section 9.4.1). Height and weight will only be measured and recorded at the Baseline Visit (before dosing).
- h. See Section 6.2 for electrocardiogram exclusion criterion for participants aged ≥ 12 to < 18 years. For additional details see Section 8.1.2 and Section 9.4.3.
- i. Take measurement of temperature, blood pressure, and pulse rate. See Section 9.4.2.
- j. If serology testing was performed within 3 months prior to the first dose of study treatment and results were **positive**, testing at Baseline **is not required**. If testing was performed within 3 months and any result was **negative**, testing at Baseline **is required**.
- k. For women of childbearing potential, a negative urine pregnancy test is sufficient for eligibility. See Appendix 6 for Baseline urine test sensitivity requirements and associated contraception requirements.
- l. During the Baseline Visit, participants randomly assigned to gepotidacin will receive their first oral dose (3000 mg) at the study site. Participants will self-administer their second dose (3000 mg) as an outpatient 10 to 12 hours after the first dose; however, for participants who weigh < 50 kg or have moderate renal impairment, the second dose should be taken approximately 12 hours after the first dose). See Section 7.1. Each dose should be taken after food consumption and with water to assist with tolerability. Participants will be contacted to confirm that they took their second gepotidacin dose. See Section 7.6.

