 - Demographic data such as year of birth, sex, sexual orientation, race, and ethnicity will be recorded in the participant's eCRF. The collection of sex, sexual orientation, race, and ethnicity data is necessary to assess and monitor the diversity of the trial participants, and to determine if the trial participants are truly representative of the impacted population. The year of birth is collected to stratify the population.
 - The participant's medical/surgical history will be obtained by interviewing the participant and/or the participant's legally authorized representative and/or review of the participant's medical records. Any pre-existing conditions, signs and/or symptoms present prior to the first dose of study treatment will be recorded in the eCRF.
 - Pretreatment baseline specimens for microbiological testing will be collected as described in Section 9.1 and Table 2.
 - Following completion of all pretreatment assessments, eligible participants will be randomly assigned to treatment as described in Section 7.3.
 - The first oral gepotidacin dose (3000 mg) or the IM ceftriaxone dose (500 mg) plus the oral azithromycin dose (1 g) will be administered at the study site. Oral study treatment (gepotidacin and azithromycin) should be taken after food consumption and with water to assist with tolerability. After dose administration, Day 1 posttreatment assessments will be performed, as shown in Table 1. Any AEs or clinically significant changes should be followed accordingly.
 - Participants randomly assigned to gepotidacin will self-administer the second 3000-mg oral dose as an outpatient 10 to 12 hours after the first dose; however, for participants who weigh <50 kg or have moderate renal impairment, the second dose should be taken approximately 12 hours after the first dose. Gepotidacin study treatment should be taken after food consumption and with water to assist with tolerability. **Note:** The second dose may occur on Day 1 or Day 2, depending on the time at which the first dose was taken. Participants randomly assigned to gepotidacin will be contacted to confirm that they took their second gepotidacin dose (see Section 7.6).

- The TOC and Follow-up Visits should be scheduled before the participant leaves the study site on Day 1 (as indicated in Table 1); the planned return day/time should be at the convenience of the participant and also the availability of the study site staff.

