9.2.3. Follow-up of AEs and SAEs

After the initial AE/SAE report, the investigator is required to proactively follow each participant at subsequent visits/contacts. All SAEs and nonserious AEs of special interest (as defined in Section 9.2.5) will be followed until the event is resolved, stabilized, otherwise explained, or the participant is lost to follow-up (as defined in Section 8.3). Further information on follow-up procedures is given in Appendix 4.

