9.3. Treatment of Overdose

In the ceftriaxone plus azithromycin treatment group, only 1 dose of ceftriaxone and 1 dose of azithromycin are administered during the study, and both are administered at the study site. Although 2 doses of gepotidacin will be administered in the study, participants will not have access to more than the required gepotidacin dose at each dosing time point. At the Baseline Visit, the first gepotidacin dose is administered at the study site and the study site staff will dispense to the participant only the number of tablets required for the second dose (self-administered as an outpatient 10 to 12 hours after the first dose). Therefore, overdoses of either study treatment are not anticipated in this study.

There is no specific antidote for overdose with a bacterial topoisomerase inhibitor. In the event of a suspected overdose, it is recommended that the appropriate supportive clinical care should be instituted, as dictated by the participant's clinical status.

There is no specific antidote for an overdose of ceftriaxone or azithromycin. Treatment of an overdose should be symptomatic (refer to the locally approved ceftriaxone and azithromycin prescribing information).

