- The investigator or his/her representative will explain the nature of the study to the participant or his/her legally authorized representative and answer all questions regarding the study. Participants should advise their sexual partner of their infection; this will be discussed with participants as part of the informed consent process and will be documented in the medical chart by the study site staff.
- Participants must be informed that their participation is voluntary. Participants or their legally authorized representative will be required to sign a statement of informed consent and/or eConsent (if applicable) that meets the requirements of 21 CFR 50, local regulations, ICH guidelines, Health Insurance Portability and Accountability Act (HIPAA) requirements, where applicable, and the IRB/IEC or study site.
- The medical record must include a statement that written informed consent and/or eConsent (if applicable) was obtained before the participant was enrolled in the study and the date informed consent was obtained. The authorized person obtaining the informed consent must also sign the ICF.
- Participants must be re-consented to the most current version of the ICF(s)/eConsent during their participation in the study.
- A copy of the ICF(s)/eConsent must be provided to the participant or the participant's legally authorized representative.
 - Adolescent participants should be asked for their written assent or eConsent (if applicable) to participate in the study.
 - As applicable, the IRB/IEC will be consulted before assent form development for guidance around age-appropriate groupings and any specific IRB/IEC requirements or local laws for conducting and documenting assent.

Participants who are rescreened are required to sign a new ICF or provide eConsent (if applicable).

Study Conduct Materials and Support

The following vendors will be used to support study conduct, translations, participant recruitment, stipends, and transportation:

Vendor Name	Vendor Service
Medable	Telemedicine and teleconsent provider
Proforma ProClinix	Central advertising/printing/patient recruitment materials
Signant Health	Patient Texting Service
Transperfect	Translations (including labels & patient cards)
TAKSEE	Patient Transportation in Spain
SERMES	Patient Reimbursement in Spain
Jumo Health	Study Website

Data Protection

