10. BENEFIT/RISK

Forest plots showing the treatment effect and confidence intervals related to benefits and risks of treatment with gepotidacin will be created. Benefits will be represented by risk differences and corresponding confidence intervals from the following analyses based on the Micro-ITT analysis population:

- Microbiological outcome and response rate of urogenital Gonorrhea at the TOC Visit (primary analysis),
- NAAT outcome and response rate of urogenital Gonorrhea at the TOC Visit (exploratory analysis).

For these analyses, risk differences and 95% confidence intervals will be determined using the methods described in Section 7.1.6.1 and Section 7.3.1.5, respectively. Additionally, relative risks and corresponding 95% confidence intervals will be displayed for the following safety endpoints: incidence of AEs, SAEs and, separately, CV, GI, *C. difficile*, and AChE-I AESIs using the Safety analysis population. Confidence intervals for relative risks will be determined using the asymptotic Wald method.

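### The second-dose contact goes to gepotidacin participants only, which gives that arm an unmatched chance to volunteer adverse events that the SAP then compares between arms

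*Protocol*

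**What the plan says.** **The contact.** Gepotidacin participants take their second dose at home. Protocol Section 7.6 says: "Compliance with gepotidacin will be assessed by contacting the participant via telephone, email, or text message". Table 1 footnote l, which concerns gepotidacin dosing, repeats it: "Participants will be contacted to confirm that they took their second gepotidacin dose". Section 9 likewise limits it to participants randomized to gepotidacin. Section 7.6 adds a second question at TOC: "Study site staff will also query the participant during the TOC Visit and document whether the second dose was taken". No passage says when the contact is made, gives a script, or says what to do with an AE mentioned during it.

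**The comparator.** Section 9.3 explains why no such contact is needed: "only 1 dose of ceftriaxone and 1 dose of azithromycin are administered during the study, and both are administered at the study site". No other contact in the first days after dosing is described for that arm.

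**AE collection.** Table 1 and Section 9.2.1 set the same AE time points for both arms: Day 1 after dosing, TOC, Follow-up and Early Withdrawal. The second-dose contact is not among them. Both arms get a reminder about 24 hours before TOC (Table 1 footnote q).

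**Use of the AE data.** The SAP presents relative risks with 95% Wald intervals for common AEs (Section 8.1) and for acetylcholinesterase-inhibition events (Section 8.2.3). It also uses relative risks to screen for potential adverse reactions (Section 8.5.2). For the benefit/risk figure, Section 10 states: "relative risks and corresponding 95% confidence intervals will be displayed for the following safety endpoints". The safety estimand itself (Protocol Table 3) is a proportion in each arm separately.

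**The concern.** A between-arm relative risk assumes that an event has the same chance of being recorded in either arm. Here one arm has one more exchange with site staff than the other, and its subject invites an account of how the participant feels. A participant who did not take the second dose has stopped treatment early. Protocol Section 8.1 lists an AE among the possible reasons for stopping and requires the reason in the eCRF.

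Section 3.3.1 names nausea, vomiting and diarrhea among the common or cholinergic-type events with gepotidacin, and calls most of the cholinergic-type ones mild and transient. Such events are plausibly the easiest to forget by a visit 3 to 7 days later. Sites know the assignment (Section 7.4). Section 9.2.2 asks for care not to bias AE detection but gives no wording for this contact.

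At stake is whether a modest excess of recorded AEs with gepotidacin can be read as a tolerability difference. Section 3.3.2 expects that gepotidacin may be better tolerated, so the asymmetry works against the sponsor's own expectation. Nothing now planned would show how much of an observed excess came from the contact.

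**Working it through.** **1. The plan's own safety figure.** SAP Section 8.5.2 gives a 90% chance of seeing at least one event among 310 gepotidacin participants at a true incidence of 0.75%. Check: 1 − (1 − 0.0075)^310 = 0.903, which reproduces it. The 310 per arm used below is 620 / 2 (Protocol Section 10.2.1, 1:1 allocation).

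**2. Model of unequal reporting.** The documents give no reporting rates, so these are assumptions:
- true incidence is equal in both arms;
- r = chance that an early AE is reported at TOC, the same in both arms;
- c = chance that it is mentioned at the second-dose contact (gepotidacin only);
- the two reports are independent.

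Recorded share: comparator r; gepotidacin 1 − (1 − r)(1 − c).
Apparent relative risk = [1 − (1 − r)(1 − c)] / r.

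| r | c = 0 | c = 0.10 | c = 0.25 | c = 0.50 |
|---|---|---|---|---|
| 0.9 | 1.00 | 0.91/0.9 = 1.01 | 0.925/0.9 = 1.03 | 0.95/0.9 = 1.06 |
| 0.8 | 1.00 | 0.82/0.8 = 1.03 | 0.85/0.8 = 1.06 | 0.90/0.8 = 1.13 |
| 0.7 | 1.00 | 0.73/0.7 = 1.04 | 0.775/0.7 = 1.11 | 0.85/0.7 = 1.21 |

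The most the mechanism can produce is 1/r, when every early event is mentioned at the contact. At r = 0.8 that ceiling is 1.25.

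**3. The adverse-reaction screen.** SAP Section 8.5.2 shortlists a term if the lower confidence limit exceeds 1, if the relative risk is at least 1.25 (control incidence 5% or more), or if it is at least 1.50 (control below 5%). With no control events, the rule is at least 3 gepotidacin participants. I applied these rules by exact binomial summation, with 310 per arm, true incidence 15% in both arms and r = 0.8. The recorded comparator incidence is then 0.15 × 0.8 = 12.0%.

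| c | Recorded gepotidacin incidence | Chance of shortlisting with no true difference |
|---|---|---|
| 0 | 12.0% | 15.8% |
| 0.10 | 0.15 × 0.82 = 12.3% | 18.5% |
| 0.25 | 0.15 × 0.85 = 12.75% | 23.0% |
| 0.50 | 0.15 × 0.90 = 13.5% | 31.5% |

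The first row is the screen's ordinary false-positive rate at that incidence and owes nothing to the contact.

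**4. Where the screen figures apply.** SAP Section 8.5.2 places every AE of special interest on the short list automatically. Section 8.2.2 defines the gastrointestinal ones by system organ class, and acetylcholinesterase-inhibition events are also of special interest (Section 8.2). Nausea, vomiting and diarrhea are therefore shortlisted whatever their relative risk. Step 3 concerns other terms only. For the gastrointestinal and cholinergic events, step 2 applies to the displayed relative risks (SAP Sections 8.1, 8.2.3 and 10).

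**5. What excluding contact-first events would show.** Gepotidacin events left after the exclusion are those reported at TOC but not at the contact, a share r(1 − c). Their relative risk is r(1 − c)/r = 1 − c. At r = 0.8 and c = 0.25 the two tables would show 1.06 and 0.75 around a true value of 1.00. The exclusion overcorrects, so it is a bound and not a corrected estimate.

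**The case against.** The strongest reply is that this is a yes/no dose check, possibly one text message, that follows unavoidably from comparing a self-administered second dose with dosing at the site. Both arms get the reminder, may return before TOC because of AEs, and are questioned at TOC with open-ended questions preferred. People who volunteer symptoms by text would probably report them at TOC too. That breaks independence and makes the effect smaller than in step 2. The relative risks are descriptive, SAP Section 8.5.1 calls the screen an aid to medical judgment, and a qualitative causality review follows. Any bias runs against gepotidacin, so it would not hide harm. All of this stands. It limits the size and consequence but does not remove the asymmetry.

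Four stronger readings are tempting and not supported:
- **That the contact is an AE assessment at which AEs must be recorded.** Section 9.2.3 says "the investigator is required to proactively follow each participant at subsequent visits/contacts", but only after an initial AE report, so it governs follow-up and not ascertainment.
- **That onset times are better in the gepotidacin arm.** The contact's timing is not stated, and one made just before TOC would add little.
- **That gastrointestinal or cholinergic events would be falsely shortlisted.** They enter the list automatically.
- **That comparator participants have no contact between Day 1 and TOC.** They get the reminder; what they lack is the second-dose contact.

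**Conclusion.** The point holds as a modest one. The one-arm contact and the between-arm relative risks are both documented. The link between them is an inference: an unscripted exchange in an open-label trial is an opportunity to volunteer AEs, and nothing in the plan matches or measures it. The direction, if there is any effect, is toward more AEs recorded with gepotidacin.

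The size cannot be derived from the documents. With 80% reporting at TOC, the apparent relative risk runs from 1.00 (nothing mentioned at the contact) to 1.13 (half of early AEs mentioned). The upper end needs a high yield from a dose-confirmation message, and independence makes these figures more likely too large than too small. What is exposed is the descriptive relative risks for AEs and the screen for terms that are not of special interest. The per-arm safety proportions are affected only in that gepotidacin may be more fully captured. The primary efficacy conclusion, which rests on culture, is untouched.

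**What to change.** **Preferred.** In Table 1 and Section 7.6, give both arms a contact at the same stated time after the first dose, with identical neutral wording, and add the second-dose question for gepotidacin only. Appendix 3 already lists a vendor for a "Patient Texting Service", although its scope is not described. The cost is a protocol wording change, about 310 extra messages (620 / 2), replies that sites must handle, and probably a few more mild AEs recorded in the comparator arm.

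**Alternative.** Keep the contact for gepotidacin only, record in the eCRF which AEs were first learned of there, and repeat the AE relative-risk tables without them. State in the SAP that the repeat is a bound, because some of those AEs would also have been reported at TOC. The cost is one eCRF field and one repeat table. This does not remove the asymmetry, but it shows whether it is large enough to matter.
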